8.2.6.3 Follow-up of AEs

After the initial AE report, the Investigator is required to proactively follow each participant at subsequent visits/contacts. All SAEs and AESIs (Section 8.2.8) will be followed until resolution, stabilization, the event is otherwise explained, or the participant is lost to follow-up (as defined in Section 0). Further information on follow-up procedures is provided in Section 10.3.3.

8.2.6.4 Regulatory Reporting Requirements for SAEs

Prompt notification of a SAE by the Investigator to the Sponsor (via PPD Pharmacovigilance) is essential so that regulatory obligations and ethical responsibilities towards the safety of participants and the safety of the IMP under clinical investigation are met. The Sponsor has a legal responsibility to notify both the local regulatory authority and other regulatory agencies about the safety of the IMP under clinical Investigation. The Sponsor will comply with country-specific regulatory requirements relating to safety reporting to the regulatory authority, IRB/IEC, and Investigators.

Investigator safety reports will be prepared for suspected unexpected serious adverse reactions (SUSAR) according to local regulatory requirements and Sponsor policy and forwarded to Investigators as necessary.

An Investigator who receives an Investigator safety report describing a SAE or other specific safety information (eg, summary or listing of SUSARs) from the Sponsor will review and then file it as appropriate and will notify the IRB/IEC, if appropriate, according to local requirements.

8.2.7 Pregnancy

Details of all pregnancies in female participants and female partners of male participants will be collected after first dose of study drug and until 30 days after the last dose as outlined in Section 10.5.3. If a pregnancy in a female participant or the partner of a male participant is reported, the Investigator should inform the Sponsor within 24 hours of learning of the pregnancy and should follow the procedures outlined in Section 10.5.3. Abnormal pregnancy outcomes (eg, spontaneous abortion, fetal death, stillbirth, congenital anomalies, ectopic pregnancy) are considered SAEs.

8.2.8 Adverse Events of Special Interest

The following AEs, which have been reported with antibody inhibition of IL-17 signaling, will be documented as AESIs:

- New onset of IBD including ulcerative colitis or Crohn's disease
- Suicidal ideation

AESIs will be reported to PPD Pharmacovigilance within 24 hours after awareness at the study site.

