2.4 Benefit/Risk Assessment

It is likely that participants in this study will benefit from the treatment with DC-806 as it has the potential to be highly efficacious with an acceptable safety profile for the treatment of moderate-to-severe plaque psoriasis. DC-806 is as an inhibitor of IL-17AA and IL-17AF and is being developed as an oral treatment for moderate-to-severe psoriasis. The IL-17/IL-17 receptor signaling pathways are well-characterized pharmaceutical targets for the treatment of psoriasis. DC-806 demonstrated acceptable PK, PD, and preclinical toxicology properties that support development of the compound. In the Phase 1 study DCE806101, DC-806 demonstrated a favorable tolerability, safety, PK, and PD profile when ascending doses were administered to healthy participants for up to 7 days and to participants with psoriasis for up to 28 days. An exploratory analysis of efficacy showed clinically relevant improvement in psoriasis disease activity after administration of DC-806 for up to 28 days, thus supporting this study in participants with moderate to severe psoriasis.

IL-17 inhibitors have been associated with risk of serious infections and opportunistic infections. In addition, participants receiving IL-17 inhibitors may develop or experience worsening of Crohn's disease or ulcerative colitis (Ixekizumab [TALTZTM] Prescribing Information 2022; Secukinumab [COSENTYX[®]] Prescribing Information 2021; brodalumab [SILIQ[®]] Prescribing Information 2020). Brodalumab has been associated with increased risk of suicidal ideation and behavior and there are also theoretical considerations linking immunomodulation with the development of malignant tumors. To minimize these potential risks, participants with the following medical conditions will be excluded: chronic infections including HIV or viral hepatitis (HBV, HCV), active TB, acute infections; and active suicidal ideation or suicide behavior. In addition, a history of malignancy or lymphoproliferative disease except resected cutaneous squamous cell or treated basal cell carcinoma will also be exclusionary.

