9.6 Independent Data Monitoring Committee

Safety and tolerability of study drug will be determined by the IDMC.

The IDMC will be established to monitor data on an ongoing basis to ensure the continuing safety of participants enrolled in this study, to ensure the integrity of the blinded nature of the study, and to oversee the planned interim analyses. An IDMC charter will be developed that will specify the roles and responsibilities of the members and interim decision rules. The Sponsor Steering Committee will receive and act on the recommendations from the IDMC. A firewall will be established to ensure the maintenance of the study blind for the Sponsor, the investigational site staff, and study participants and their study partners.

Data summaries and listings will be provided to the IDMC to facilitate their safety assessment at the regularly scheduled times and on an ad hoc basis if needed. The safety review includes serious AEs and AESIs, focusing on early signal detection. Further details on the frequency, content, and methods of data reports to the IDMC will be outlined in the charter of that committee along with the processes and procedures the committee will follow.

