#### 9.1.4. Adverse Events of Special Interest

An adverse event of special interest (AESI) (serious or nonserious) is defined as an AE or SAE of scientific and medical concern specific to the Sponsor's product or program, for which ongoing monitoring and rapid communication by the Investigator to the Sponsor could be appropriate. The following events will be considered AESIs for this study and will be reported using the same process as for SAEs:

- New onset of inflammatory bowel disease (IBD) including ulcerative colitis or Crohn's disease
- Suicidal ideation

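### The AESI list omits suicidal behavior and opportunistic infections, both named as risks in Protocol 2.4, so the non-serious cases have no 24-hour report and no AESI table entry

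*Protocol*

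**What the plan says.** Protocol 8.2.8 opens its list with "The following AEs, which have been reported with antibody inhibition of IL-17 signaling, will be documented as AESIs". Two items follow: "New onset of IBD including ulcerative colitis or Crohn's disease" and "Suicidal ideation". The reporting rule is "AESIs will be reported to PPD Pharmacovigilance within 24 hours after awareness at the study site". SAP 9.1.4 carries the same two items and says "The following events will be considered AESIs for this study and will be reported using the same process as for SAEs".

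The benefit/risk section, Protocol 2.4, names more risks. On psychiatric events it says "Brodalumab has been associated with increased risk of suicidal ideation and behavior". On infection it says "IL-17 inhibitors have been associated with risk of serious infections and opportunistic infections".

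For the data monitoring committee, Protocol 9.6 says "The safety review includes serious AEs and AESIs, focusing on early signal detection" and leaves the frequency and content of reports to the charter.

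**The concern.** The AESI list is shorter than the risk statement behind it. The sentence in Section 2.4 that supports listing suicidal ideation names behavior together with it, yet only ideation was carried into 8.2.8. Opportunistic infection, which 2.4 attributes to IL-17 inhibitors generally, was not carried over at all. Neither document explains either choice.

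AESI status has practical effects. It brings a 24-hour report whether or not the event is serious. It brings a separate overall AESI summary, a table by preferred term and a listing (SAP 9.1.1). It brings follow-up to resolution or stabilization (Protocol 8.2.6.3) and places the event in the content that 9.6 names for the committee. An event that is neither an SAE nor an AESI gets none of these by right. Safety and tolerability are a primary objective, so a named risk should not depend on the seriousness judgment alone to be noticed early.

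**Working it through.** The documents give no rate or count for these events, so there is nothing to calculate. The check is to follow each type of event through the text.

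**Inputs**

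- AESI list and its 24-hour rule: Protocol 8.2.8 and SAP 9.1.4.
- SAE route after first dose: Protocol 10.3.5.2 puts AESIs and SAEs on one route with one 24-hour limit.
- SAE criteria: Protocol 10.3.2, including the clause on important medical events, which rests on judgment.
- Intentional overdose: Protocol 10.3.1.1 makes overdose with possible suicidal or self-harming intent reportable whatever its consequences.
- Committee content: Protocol 9.6.

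**Result by type of event**

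| Event | 24-hour report | AESI tables | In the content named in 9.6 |
|---|---|---|---|
| Suicidal ideation, serious or not | Yes, as AESI | Yes | Yes |
| Suicidal behavior with ideation also recorded | Yes, through the ideation | Yes, as ideation | Yes, through the ideation |
| Suicidal behavior meeting an SAE criterion | Yes, as SAE | No | Yes, as SAE |
| Suicidal behavior judged non-serious, no ideation recorded | No | No | No |
| Infection meeting an SAE criterion | Yes, as SAE | No | Yes, as SAE |
| Non-serious opportunistic infection | No | No | No |

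The fourth and sixth rows are the gap. For the fourth, an example is a preparatory act or an aborted attempt that the investigator does not class as an important medical event.

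**Do other provisions close it?**

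- *Columbia scale.* It is given at every visit (Protocol 1.3), and SAP 9.7 tabulates suicidal behavior by treatment group. That serves the study analysis. Protocol 8.2.5.6 does not send a positive behavior item onward within 24 hours.
- *Withdrawal rule.* Protocol 7.1 requires referral and withdrawal for any suicidal behavior. This protects the participant but sets no reporting clock. It also shows that the protocol regards behavior as at least as grave as ideation.
- *General adverse event tables.* SAP 9.1.1 tabulates all treatment-emergent events by system organ class and preferred term, so infections appear there. These tables do not single out opportunistic infections and are not a rapid route.
- *Follow-up.* Protocol 8.2.6 covers events that are serious, related or led to discontinuation. A non-serious opportunistic infection judged unrelated, with study drug continued, lacks the assurance given to AESIs.

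**The case against.** The best defense has four parts.

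*Serious events are already expedited.* This stands. A reader might infer that the graver psychiatric event is reported more slowly than the milder one. The documents do not support that. Behavior that is fatal, life-threatening, leads to hospitalization or is judged an important medical event goes by the SAE route on the same 24-hour clock. The important-medical-event clause may capture many attempts.

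*The list need not be exhaustive.* The opening words of 8.2.8 can be read as describing the two items rather than promising every event reported with IL-17 antibodies. SAP 9.1.4 does not state that criterion; it defines AESIs by their concern for the sponsor's product or program. This also stands: the list is a sponsor's choice and not a formal contradiction. The choice still has no stated reason.

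*Suicidality is tied to one agent.* Section 2.4 names brodalumab, so calling suicidal behavior a class risk would overstate the text. But ideation is on the list, and the same sentence names behavior with it. The point does not explain why only one was kept.

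*The committee may see these events anyway.* Section 9.6 says what the review includes, which is not exclusive. The charter and separate committee shells (SAP Section 1) set the content, and Protocol 2.4 says the committee reviews unblinded safety data. It would therefore be wrong to conclude that the committee will miss these events. What can be said is that neither document guarantees them.

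**Conclusion.** The point holds in a limited form. Protocol 8.2.8 and SAP 9.1.4 do not match the risks named in Protocol 2.4, and no reason is given. Two kinds of event are affected: suicidal behavior judged non-serious and recorded without ideation, and non-serious opportunistic infection. Both lack a 24-hour report, an AESI table entry and a named place in the committee's review.

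The number of such events cannot be derived from the documents and may be small. The conclusion assumes that some suicidal behavior would be judged non-serious, and that the charter, which is not among the documents, does not already require these events. If investigators treat all suicidal behavior as an important medical event, the psychiatric part of the gap closes in practice and the infection part remains. Sample size and the efficacy analysis are not touched. This is a modest consistency point, worth making because the correction is cheap.

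**What to change.** In Protocol 8.2.8 and SAP 9.1.4, replace the item on suicidal ideation with suicidal ideation or behavior, and add opportunistic infections. Define the latter by a MedDRA term list fixed in advance, because the term is otherwise open to interpretation. Give sites a plain list of the matching diagnoses, since they must recognize the event before it is coded. The AESI tables and listing in SAP 9.1.1 then pick up the added events. State in the committee's charter that both are in its listings; the protocol wording alone does not ensure this. If the sponsor prefers the present list, a sentence in 8.2.8 should say why suicidal behavior and opportunistic infections are left off.

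The cost is a protocol and SAP wording change, a short term list and a few more 24-hour reports. Treatment, eligibility, sample size and the efficacy analysis are unchanged. Expedited reporting can only start once the amendment is in force, but the AESI tables can apply the wider definition to all adverse events recorded in the study.

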8.3 Treatment of Overdose

There is no antidote for DC-806. In the advent of an adverse reaction due to an overdose (ie, taking more than the prescribed number of tablets), supportive and symptomatic treatment is indicated relevant to the clinical scenario. In serious cases, participants should be hospitalized for observation and/or further intervention as necessary.

8.4 Pharmacokinetics

Venous blood samples will be withdrawn via an indwelling cannula or by venipuncture. Samples will be collected into appropriate tubes as specified by the bioanalytical laboratory. Details for collection and processing procedures for PK samples are provided in the Laboratory Manual.

Plasma samples will be processed from venous blood and analyzed according to a validated method. Analytical methods are validated according to internationally accepted standards. The quality and integrity of the analytical work generated in this study will be evaluated in accordance with the study plan, validated method, and standard operating procedures (SOPs) of the bioanalytical laboratory.

8.5 Pharmacodynamics

Venous blood samples will be withdrawn via an indwelling cannula or by venipuncture. Samples will be collected into appropriate tubes as specified by the bioanalytical laboratory. Details for collection and processing procedures for PD samples are provided in the Laboratory Manual.

Serum samples will be processed from the venous blood and will be analyzed according to the bioanalytical laboratory's methods. The quality and integrity of the analytical work generated in this study will be evaluated in accordance with the study plan and SOPs of the bioanalytical laboratory.

8.5.1 Blood Sampling

Venous blood samples will be withdrawn via an indwelling cannula or by venipuncture. Samples will be collected into appropriate tubes as specified by the bioanalytical laboratory. Details for collection and processing procedures for blood samples are provided in the Laboratory Manual.

8.5.2 Skin Plaque Biopsy

Skin plaque biopsies (punch biopsies) will be collected from participants at selected study sites according to the Schedule of Assessments (Section 1.3). Details of skin plaque biopsy collection will be provided in the Study Reference Manual.

Biopsies will be analyzed for exploratory PD biomarkers including immunohistochemistry assessment of biopsy tissues (including but not limited to hematoxylin and eosin staining) and mRNA levels relevant to the IL-17 pathway and psoriasis, including but not limited to gene expression level of selected IL-17 pathway related genes.

9.0 STATISTICAL CONSIDERATIONS

A SAP will be prepared and finalized before database lock and analysis of data. Any deviations from the final SAP will be described and justified in the study report. All statistical analyses will be performed using Statistical Analytics Software (SAS®).

Continuous data will be summarized using the number of participants, mean, standard deviation, median, minimum and maximum values, while categorical data will present the number and percentage of participants within each category. Summaries will be provided by DC-806 dose regimen and placebo). Listings of individual participant data will also be produced.

9.1 Sample Size Determination

This study will randomize approximately 225 participants with moderate to severe plaque psoriasis, with approximately 45 participants each to 1 of 4 DC-806 dose regimens and approximately 45 participants to placebo.

9.2 Analyses Sets

- Enrolled Set: All participants who sign an ICF
- Full Analysis Set: All participants who are randomized and received at least 1 dose of study drug (DC-806 or placebo); participants will be analyzed as per randomized treatment and all efficacy analyses will be performed using this population
- Safety Analysis Set: All participants who received ≥1 dose of study drug (DC-806 or placebo); this population will be used for safety analyses and will be analyzed as per actual treatment received
- Pharmacokinetics Set: All participants who received any study drug (DC-806 or placebo) and have any available concentration-time data
- Biomarker Set: All participants who received any study drug (DC-806 or placebo) and have both Baseline and ≥1 post-treatment biomarker measurements

9.3 General Analyses

Full details of the statistical analyses will be provided in a separate SAP. Statistical analysis will be descriptive and exploratory. Continuous data will be summarized using descriptive statistics (n, mean, standard deviation, median, minimum, and maximum) and categorical data will be summarized using the number and percentage of participants in each category. Where confidence limits are appropriate, the confidence level will be 95% (2-sided), unless otherwise stated. Data will be presented by treatment group. Unless otherwise stated, for the purposes of summaries and analyses, Baseline will be defined as the last nonmissing assessment value before the first dose of study drug. Further details regarding selection of Baseline for specific endpoints will be given in the SAP.

9.3.1 Demographic Data and Baseline Characteristics

Demographics and Baseline characteristics (including age, sex, race, ethnicity, height, weight, and BMI), medical history, baseline disease activity, and prior/concomitant medication will be summarized by DC-806 dose regimen and placebo using descriptive statistics. Concomitant medications will be coded using the most current World Health Organisation Drug Dictionary in place at the time of study start. Baseline characteristics refer to those collected at Screening.

9.3.2 Safety Analysis

Safety will be evaluated by presenting summaries of AEs, vital signs, physical examination findings, ECGs, and clinical laboratory evaluations. Safety variables will be tabulated by DC-806 dose regimen and placebo.

Adverse events will be coded using the MedDRA®. The incidence proportion of TEAEs will be presented by system organ class and preferred term, by relationship to study drug, by severity, and by whether or not they resulted in alteration of administration of or discontinuation of study drug. A TEAE is defined as an AE that occurs during or after the first study drug infusion and up to and including the Follow-up Visit. In addition, the incidence proportion of serious TEAEs and TEAEs leading to discontinuation of study drug will be presented by system organ class, preferred term, and relationship to study drug.

Vital signs and clinical laboratory test results will be listed and summarized by treatment. Any significant physical examination findings and clinical laboratory results will be listed. ECG readings will be evaluated by the Investigator and abnormalities, if present, will be listed.

9.3.3 PK Analysis

Summary statistics will be tabulated for C_{max} or C_{trough} levels at different time points. Additional details will be provided in the SAP as necessary.

9.3.4 PD Analysis

Serum concentrations of inflammatory cytokines (eg, IL-17, IL-19, and potentially other IL-17 pathway and psoriasis biomarkers) and gene expression levels of multiple IL-17 pathway related markers in skin before and after DC-806 treatment will be analyzed as exploratory assessments. These analyses are outside the scope of the study SAP.

9.3.5 Efficacy Analyses

9.3.5.1 Primary Efficacy Analyses

PASI-75 score after 12 weeks of treatment will be analyzed using 2-sample Fisher's exact test or Chi-squared test based on observed count to compare response rates in DC-806 dose regimens and placebo.

The odds ratio (odds in a treatment group/odds in placebo group) in the response rates and its corresponding 2-sided 95% CI will be provided.

9.3.5.2 Secondary Efficacy Analyses

Similar analyses as in primary efficacy analyses will be performed to compare any 2 DC-806 dose regimens.

A Cochran-Armitage trend test will be conducted to assess a positive trend between DC-806 dose regimens and PASI-75 at Week 12.

The response rate in PASI-50, PASI-75, PASI-90, and PASI-100 will be summarized by treatment group and visit and will be analyzed using a repeated measure model when applicable.

The proportion of participants with an sPGA score of "0" or "1" will be analyzed similarly to the primary analyses. sPGA and DLQI score will be tabulated by treatment group and visit; the corresponding changes from Baseline and percent change from Baseline will be calculated and summarized.

For continuous secondary endpoints (eg, change from Baseline to Week 12 in PASI scores), point estimates and 2-sided 95% CIs for mean change from Baseline within each treatment group will be provided. For binary endpoints (eg, response rate in PASI and sPGA), point estimates of the response rate and 2-sided 95% CIs will be provided using normal approximation within each treatment group.

There will be no adjustment for multiplicity. All comparisons will be performed in a prespecified hierarchical procedure starting from the highest dose regimen to the lowest dose regimen.

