- Pharmacokinetics Set: All participants who received any study drug (DC-806 or placebo) and have any
 available concentration-time data
- Biomarker Set: All participants who received any study drug (DC-806 or placebo) and have both Baseline and ≥1 post-treatment biomarker measurements

Demographics and Baseline Characteristics

Demographics and Baseline characteristics, including baseline disease activity, will be tabulated by DC-806 dose regimen and placebo using descriptive statistics.

Primary Efficacy Analyses

PASI-75 score after 12 weeks of treatment will be analyzed using 2-sample Fisher's exact test or Chi-squared test based on observed count to compare response rates in DC-806 dose regimens and placebo.

The odds ratio (odds in a treatment group /odds in placebo group) in the response rates and its corresponding 2-sided 95% confidence interval (CI) will be provided.

In addition, a logistic regression model may be performed to incorporate some of the covariates if they are assumed to impact the response rates. Details of the tests and models will be provided in the SAP.

Secondary Efficacy Analyses

Similar analyses as in primary efficacy analyses will be performed to compare any 2 DC-806 dose regimens. A Cochran-Armitage trend test will be conducted to assess a positive trend between DC-806 dose regimens and PASI-75 at Week 12.

The response rate in PASI-50, PASI-75, PASI-90, and PASI-100 will be summarized by treatment group and visit and will be analyzed using a repeated measure model when applicable. CCl

The proportion of participants with an sPGA score of "0" or "1" will be analyzed similarly to the primary analyses. sPGA and DLQI score will be tabulated by treatment group and visit; the corresponding changes from Baseline and percent change from Baseline will be calculated and summarized.

For continuous secondary endpoints (eg, change from Baseline to Week 12 in PASI scores), point estimates and 2-sided 95% CIs for mean change from Baseline within each treatment group will be provided. For binary endpoints (eg, response rate in PASI and sPGA), point estimates of the response rate and 2-sided 95% CIs will be provided using normal approximation within each treatment group.

There will be no adjustment for multiplicity. All comparisons will be performed in a prespecified hierarchical procedure starting from the highest dose regimen to the lowest dose regimen.

Confidential Page 12 of 91

Safety Analyses

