#### 4. General Statistical Considerations

Data collected in this study will be presented using summary tables, participant data listings and figures. For ordinal-scaled variables, a combination of presentations may be employed as appropriate: frequency and percentage of observations within a category and means and standard deviations of the scores of the categories. For categorical and ordinal variables, percentages will be calculated based on the N of the analysis set and number of participants with missing data will also be included. All by-visit summaries will use assessments done at the scheduled visits. If multiple assessments or measurements are done at a single scheduled visit, only the latest such assessment/measurement will be included in the summary. All data will be included in the listings.

Continuous variables will be summarized using the number of participants, mean, standard deviation (SD), median, minimum, and maximum values. The minimum and maximum values will be presented to the same level of precision as the data. The mean and median will be presented to one decimal place greater than the level of precision in the data, and the SD will be presented to two decimal places greater than the level of precision in the data. Categorical summaries will include the frequency counts of each category, and the percentage displayed to one decimal place. In the case of a zero count, the percentage will be suppressed to draw attention to the non-zero counts.

Unless otherwise specified, all confidence intervals (CI) will be 2-sided and performed using a 5% significance level. P-values will be displayed in the following format: 0.9999. Any p-value less than 0.0001 will be displayed as <0.0001. Any p-value greater than 0.9999 will be displayed as >0.9999.

The reference date for the calculation of study days will be the date of the first dose at Day 1. For events/assessments on or after the treatment start date, the study day of events/assessments from treatment start date is calculated as the date of event minus the reference date + 1. For events/assessments before the treatment start date, the study day of events/assessments is defined as the date of assessment minus the reference date.

Baseline will be defined as the last non-missing assessment value before the first dose of study drug.

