#### 8.1.1. Estimand 1a

#### 8.1.1.1. Main Analysis Approach

A participant receiving any prohibited medication or discontinuing the treatment due to related adverse event or requirement for prohibited medication prior to Week 12 visit will be considered as a non-responder (Composite strategy). If a participant discontinued treatment for reasons other than related adverse event or requirement for prohibited medication, PASI scores after the treatment discontinuation date will be set to missing (Hypothetical strategy). If a participant experienced any treatment interruption, PASI score reported after the treatment interruption will be used as reported (Treatment policy).

Participants without Week 12 PASI score (either due to hypothetical strategy implementation or missed visit) will be considered as non-responder.

A 2-sided, 2-sample Fisher's exact or Chi-squared test will be performed to assess a difference between active treatment groups (DC-806) versus Placebo in PASI-75 at Week 12 for the following comparisons on the FAS:

#### Comparison 1

H0: PASI-75 at Week 12  $_{DC-806\ 800mg}$  = PASI-75 at Week 12  $_{Placebo}$ H1: PASI-75 at Week 12  $_{DC-806\ 800mg} \neq$  PASI-75 at Week 12  $_{Placebo}$ 

#### Comparison 2

H0: PASI-75 at Week 12  $_{DC-806\ 600mg}$  = PASI-75 at Week 12  $_{Placebo}$ H1: PASI-75 at Week 12  $_{DC-806\ 600mg} \neq$  PASI-75 at Week 12  $_{Placebo}$ 

#### Comparison 3

H0: PASI-75 at Week 12  $_{DC-806 400mg}$  = PASI-75 at Week 12  $_{Placebo}$ 

H1: PASI-75 at Week 12  $_{DC-806 \ 400 mg} \neq$  PASI-75 at Week 12  $_{Placebo}$ 

#### Comparison 4

H0: PASI-75 at Week 12  $_{DC-806\ 200mg}$  = PASI-75 at Week 12  $_{Placebo}$ H1: PASI-75 at Week 12  $_{DC-806\ 200mg} \neq$  PASI-75 at Week 12  $_{Placebo}$ 

The number and percentage of participants who are defined as PASI-75 responder will be presented by treatment group. The p-value and unconditional odds ratio with its corresponding 95% CI will be presented in the active treatment group compared to the placebo group. All comparisons will be performed in a prespecified hierarchical procedure starting from the highest dose regimen to the lowest dose regimen.

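### Does a dose hierarchy alongside a statement of no multiplicity adjustment leave the testing rule undefined?

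*Protocol*

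**What the plan says.** Two protocol sentences stand together, in the synopsis (1.1, Secondary Efficacy Analyses) and in 9.3.5.2: "There will be no adjustment for multiplicity. All comparisons will be performed in a prespecified hierarchical procedure starting from the highest dose regimen", down to the lowest. Protocol 9.3.5.1 gives the primary test as "exact test or Chi-squared test based on observed count to compare response rates in DC-806 dose regimens and placebo" and does not mention multiplicity.

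The SAP leaves out the no-adjustment sentence and keeps the ordering. Section 8.1.1.1 lists four placebo comparisons (800, 600, 400, 200 mg), says "A 2-sided, 2-sample Fisher's exact or Chi-squared test will be performed to assess a difference", and closes with "All comparisons will be performed in a prespecified hierarchical procedure starting from the highest dose regimen to the lowest dose regimen". Section 8.2.1.1.1 uses the same closing sentence for six comparisons between active regimens.

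On reporting, SAP 8.1.1.1 says "The p-value and unconditional odds ratio with its corresponding 95% CI will be presented in the active treatment group compared to the placebo group", with no condition on earlier steps. The 5% level in SAP section 4 is attached to intervals: "all confidence intervals (CI) will be 2-sided and performed using a 5% significance level". Protocol 9.3 sets the overall status: "Statistical analysis will be descriptive and exploratory".

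**The concern.** Read quickly, the protocol denies any multiplicity adjustment and then describes what is normally a multiplicity procedure. An order of testing protects against false positives only if a failed step has a consequence, and none is stated. The documents also do not say whether p-values after a failed step are nominal, or whether the six active comparisons come after the four placebo ones.

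Two readings then compete. If the order only governs presentation, each regimen with p≤0.05 could be described as effective. If it is a fixed sequence, one non-significant higher dose prevents that description for every dose below it. Were the choice made after unblinding, the results could influence it. At stake is which doses are described as working when regimens are chosen for later studies.

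**Working it through.** **Are the sentences compatible?** A fixed sequence tests each hypothesis at the full 0.05 and moves on only after a rejection. No alpha is split and no p-value is adjusted, so the first sentence holds. If there were no stopping, the second sentence would do nothing. The reading that gives both sentences a meaning is the fixed sequence, and SAP 8.1.1.1 lists its order.

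**Inputs.** 45 per arm with a shared placebo group (Protocol 9.1, SAP 4.2); two-sided tests, Fisher or chi-squared (SAP 8.1.1.1). The documents show no response rates, power or family-wise error rate, so there is no stated figure to reproduce. All rates below are assumptions.

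**Method.** For each pair of responder counts (0-45 in each arm), record whether p≤0.05, using Pearson chi-squared without continuity correction or two-sided Fisher. Let r_j(b) be the probability that regimen j is rejected given placebo count b, and f(b) the binomial probability of b.

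- With equal rates, r_j(b) = r(b). At least one false rejection, no stopping: Σ f(b)·[1 − (1 − r(b))⁴].
- The same with stopping: Σ f(b)·r(b), since the first test must reject.
- The two readings agree when the rejected doses form an unbroken run from the top. They differ with probability 1 − Σ f(b) Σ_{m=0..4} Π_{j≤m} r_j(b) · Π_{j>m} (1 − r_j(b)).

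**All true rates equal, four placebo comparisons.** Each cell gives no stopping / stopping. The last two columns count only rejections in favour of DC-806.

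| Assumed rate | Chi-squared, either direction | Fisher, either direction | Chi-squared, DC-806 better | Fisher, DC-806 better |
|---|---|---|---|---|
| 5% | 0.155 / 0.049 | 0.020 / 0.006 | 0.079 / 0.025 | 0.011 / 0.003 |
| 8% | 0.183 / 0.060 | 0.050 / 0.015 | 0.085 / 0.030 | 0.026 / 0.007 |
| 10% | 0.179 / 0.059 | 0.068 / 0.020 | 0.082 / 0.030 | 0.034 / 0.010 |
| 15% | 0.167 / 0.055 | 0.083 / 0.025 | 0.079 / 0.027 | 0.039 / 0.013 |
| 20% | 0.166 / 0.054 | 0.084 / 0.026 | 0.080 / 0.027 | 0.041 / 0.013 |

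Normal theory gives 0.156 and 0.050 in either direction. The last two columns matter here, because the feared error is calling a dose better than placebo.

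**Six active comparisons, regimens equal at 30-50% (simulation).** At least one false difference occurs in about 19-21% of trials by chi-squared or 12-14% by Fisher without stopping. Stopping in the listed order gives about 5% or 3%.

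**How often the readings name different doses.** Placebo 8%, superiority direction, with placebo 5% to 12% in brackets for the first three rows:

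| Assumed response, high to low dose | Chi-squared | Fisher |
|---|---|---|
| 50/40/30/20% | 4% (2-6%) | 5% (4-7%) |
| 35/35/35/20% | 13% (5-26%) | 20% (9-32%) |
| 30% in all four | 33% (16-46%) | 42% (25-47%) |
| 60/50/40/20% | 0.4% | 0.6% |

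**Cost of stopping to the lowest dose (placebo 8%).** Its chance of being called positive falls from 40% to 37% by chi-squared under 50/40/30/20%. Under a flat 30% it falls from 80% to 55% by chi-squared, or from 70% to 40% by Fisher.

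**The case for a change.** The strongest reply is that exploratory status does not settle the matter. Dose ranging for future studies is a stated purpose (Protocol 2.1), so which doses are described as effective has consequences. If every p-value is only nominal, the hierarchy is idle text; if it is not idle, its stopping rule should be written down. Similar response across regimens is also possible: Protocol 4.3 mixes once- and twice-daily dosing to study time above target, so response need not follow the listed order. That is where the two readings differ most.

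Part of this stands. The stopping rule and the label for later p-values are unwritten in the visible text, and the link between the two families is not stated. A sentence on each would have been tidier. Some sections in the contents lists are absent from the text available (Protocol 9.4, SAP 13, the SAP sensitivity and supplementary sections), so it cannot be said that the plan has no such rule anywhere.

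The rest is weaker. No visible passage defines a positive dose or a p≤0.05 criterion for carrying one forward. Protocol 4.3 points instead to exposure-response and an exposure target, over a planned trough range of about 8-fold. That makes an identical response at every regimen an extreme case, though not an impossible one. Possible remedies also point in opposite directions: stopping costs power at lower doses, and dropping the hierarchy gives up family-wise control. In an exploratory study that is the sponsor's trade-off, and neither choice is plainly better.

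**Conclusion.** No change is needed. This is a gap that analysts fill sensibly: read the listed order as a fixed sequence at two-sided 0.05, present all the p-values and intervals as the SAP already requires, and treat those after the first non-significant step as nominal.

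Estimates and intervals are the same under either reading; only the verbal description of individual doses can differ. Under equal true rates of 5-20%, the chance of wrongly calling some regimen better than placebo is about 8% against 2.5-3% by chi-squared, and 1-4% against 0.3-1.3% by Fisher. Disagreement over which doses to name is 4-5% under the graded 50/40/30/20% case and below 1% under 60/50/40/20%, both with placebo at 8%. It reaches 33-42% only under a flat 30%.

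The conclusion rests on the assumed rates, on 45 per arm, on the exploratory status in Protocol 9.3, and on there being no p-value rule for dose selection in text that is not visible. If these p-values were to carry a confirmatory claim, the stopping rule would have to be stated.
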